7.4 Primary Safety Comparison

The primary safety endpoint of this study will be the first occurrence of hospitalization for major bleeding. The primary safety analysis will be performed by the ITT principle based on randomized treatment assignment. Cumulative endpoint event rates will be estimated using Kalbfleisch & Prentice's nonparametric estimator of the CIF, taking into account the competing risk of all-cause death. Event-free survival rates will be compared using the Fine and Gray method, equivalent to the Cox proportional-hazards model when competing risks are present, using censoring rules defined in Section 7.5. Grey's test is the competing risk equivalent to the log-rank test for comparing the equality of event curves. The test will be two-tailed and will be performed at an overall α of 0.05.

7.5 Censoring Rules

In the event that a patient does not experience an efficacy or safety endpoint, the patient will be censored at the earliest of study end date or maximum follow-up time point at which the patient can be reasonably assumed to be event free. The maximum follow-up time point will be determined from any of the following data sources: CDM censor date, CMS censor date, private health insurance censor date, or the web portal censor date (last point of contact).We expect the study end date to occur on or before all follow-up time points; however, for completeness, censoring dates are defined below. Patients who withdraw consent for trial follow-up will be censored at the time consent is withdrawn. Patients who consent to limited participation follow-up will be censored at the earliest follow-up time point as delineated.

The censoring date for CDM data will be at the site-specific censoring date, which is determined by the PCORnet Distributed Research Network Operations Center based on data curation query results. The censoring date for CMS will be the minimum of the end of enrollment in fee-forservice or the last date claims data are available. The censoring date for private health insurance claims will be the minimum of the end of claims enrollment or the last date claims data are available.

Time to event modeling will include the first occurrence of an event where the time to event is calculated as the event date – randomization date +1.

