- Medical record data for hospitalizations reported by participant on the ADAPTABLE participant web portal, but not captured by queries applied to the PCORnet CDM, Medicare data, or health plan data, will be obtained by the DCRI Call Center and used to classify the specified participant-reported hospitalizations using the same endpoint coding algorithms that will be applied to the EHR data sources (PCORnet CDM, Medicare data, and health plan data—see figure below. The role of the DCRI Call Center will be especially important for the final months of the follow-up period when, due to inherent data latency associated with these data sources, Medicare data and health plan data will not yet be available for confirming out-of-network hospitalizations reported on the ADAPTABLE participant web portal. Participant-reported hospitalizations that cannot be classified by applying coding algorithms will be clinically reviewed using available medical record data obtained by the DCRI Call Center and confirmed events will be included as trial endpoints.
- Deaths occurring in-hospital at participating network hospitals will be captured with CDM queries, but deaths are often not well represented in EHR data sources, especially out-ofhospital deaths, that are expected to be the majority of the accrued death events during the trial. Medicare data do include information about death events regardless of the location of death, but only for patients enrolled in and eligible for Medicare (Medicare gathers this information from claims, reports from family members, and benefit information collected from the Social Security Administration). The DCRI Call Center will often identify death events from participant-designated alternative contacts during ascertainment of vital status when 2 or more consecutive visits are not completed in the ADAPTABLE participant web portal and/or when final contact with the participant cannot be confirmed. Additionally, the DCRI Call Center will confirm and enter death information in cases where sites notify the study team of out-of-hospital deaths. A participant-locator service may be used during the course of the study to find participants who may have been lost to follow-up. This service will be used to ensure that contact at the end of the trial is made with as many participant as possible who do not complete their final visit to the web portal or complete their final visit via telephone contact with the DCRI Call Center.

III.E.4.a. Death

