7.3 Primary Effectiveness Comparison

The primary endpoint of this study will be event-free survival from the first event of a composite of all-cause death, hospitalization for nonfatal myocardial infarction, or hospitalization for nonfatal stroke. The primary effectiveness analysis will be performed in the ITT population based on randomized treatment assignment. Event-free survival rates will be compared using Cox proportional-hazards models, equivalent to the log-rank test, using censoring rules described in Section 7.5. The test will be two-tailed and will be performed at an overall α of 0.05. The proportional hazards assumption will be checked for the randomized treatment assignment using weighted Schoenfeld residuals. If there is evidence of non-proportionality, a cautious interpretation of the Cox model hazard ratio will be encouraged, and non-parametric event rate estimates will be emphasized (see below).

In addition to Cox regression, cumulative endpoint event rates will be estimated as a function of follow-up time in each treatment group using Kalbfleisch & Prentice's nonparametric estimator of the cumulative incidence function (CIF). The Kalbfleisch & Prentice CIF estimator is equivalent to the Kaplan-Meier estimator when applied to endpoints that are not subject to competing risks. Cumulative endpoint event rates and differences in cumulative endpoint event rates will be

estimated and presented with 95% confidence intervals. These non-parametric analyses are important for descriptive purposes and will be a focus of interpretation if the event rate curves cross. They may also be used to construct summary measures of treatment effect which are interpretable when the proportional hazards assumption is violated.

Sensitivity analyses for potential misclassification and under-reporting of endpoints and for nonadherence to randomized aspirin dose are described in Section 7.10. An additional sensitivity analysis will be performed to take clustering of patients within sites into account, using the robust sandwich covariance estimator.

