For the primary analysis (and related secondary analyses), we make the following assumptions:

- Death is reported without error.
- Other components of the primary endpoint may be subject to under-reporting and misclassification but these errors are non-differential, i.e. probability of an error is consistent across randomized treatment groups.
- Patient self-report with confirmation is assumed to have nearly perfect specificity since incorrect self-reports will be excluded by examination of medical record. There may be some under-reporting since identification of the event depends on self-report. Some selfreported events may not be confirmed or contradicted if participant did not consent to confirmation process.
- CDM endpoints may be under-reported since participants may be treated for events outside the CDM health systems or events within the health system may be missed. Misclassification may occur due to imperfect electronic phenotype definitions.
- Claims data (CMS and private) is assumed to be complete for enrolled participants and changes in enrollment status are independent of trial outcome. Misclassification may occur due to imperfect electronic phenotype definitions.

We will perform two sets of sensitivity analyses: 1) to assess impact of under-reporting on the primary analysis and 2) to assess impact of misclassification on the primary analysis. Because available data sources vary across participants, we summarize the potential for error due to under-reporting and misclassification according to each potential combination of available data. To simplify classification of participants, we will not attempt to account for changes in data sources over time, but rather classify participants according to data sources available for more than half of follow-up time.

	Data sources available			Potential error		
Scenario	Self- report	Out of Network Confirmation	CDM	Claims (CMS or private)	Under- reporting	Misclassification
1	Х				Yes	Yes
2	Х	Х			Yes	No
3	х		Х		Yes	Yes
4	Х			Х	No	Yes
5	Х		Х	Х	No	Yes
6			Х		Yes	Yes
7				Х	No	Yes

8		Х	Х	No	Yes
9*				Yes	No

*Only information is vital status check at end of trial.

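### SAP 7.5 gives no censoring date to survivors known only through the vital-status check, although deaths found by that check count as events

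*SAP*

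**What the plan says.** SAP 7.5 sets one censoring rule for all efficacy and safety endpoints, and it applies only to participants without an event: "In the event that a patient does not experience an efficacy or safety endpoint, the patient will be censored at the earliest" of the study end date and the last point at which the participant can reasonably be taken as event-free. That point comes from four dates. "The maximum follow-up time point will be determined from any of the following data sources: CDM censor date, CMS censor date" gives two of them, and the list ends with "private health insurance censor date, or the web portal censor date (last point of contact". The SAP expects the rule seldom to matter: "We expect the study end date to occur on or before all follow-up time points".

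Deaths reach the analysis by a wider route. The primary endpoint in SAP 7.3 is "event-free survival from the first event of a composite of all-cause death" and two kinds of hospitalization. Protocol III.E.4 says: "The DCRI Call Center will often identify death events from participant-designated alternative contacts during ascertainment of vital status", when consecutive visits are missed or final contact cannot be confirmed. It adds deaths notified by sites and allows a participant-locator service. SAP 7.10 assumes "Death is reported without error". Its table of data-source scenarios has a row 9 with no self-report, CDM or claims, footnoted "Only information is vital status check at end of trial".

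**The concern.** One search has two possible results, and the rule treats them differently. A death is timed at its own date, however long after the last listed source. An alive result adds no follow-up unless it happens to create one of the four listed dates. Deaths stay in the numerator while survivors' later time leaves the denominator. The Cox and cumulative incidence analyses assume that censoring does not depend on the outcome, and for these participants it does.

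All-cause death is a named secondary endpoint and part of the primary composite. SAP 7.3 also makes the nonparametric event-rate estimates a focus of interpretation if the curves cross, so a distortion of absolute rates is not merely cosmetic.

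**Working it through.** **Does any other rule close the gap?**

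- SAP 7.5 times an event from its own date. Nothing limits deaths to those before the last source date.
- SAP 7.9.1 places a confirmed event with no date midway between the last event-free visit and the end of follow-up, hence after that visit.
- The tipping-point analysis in SAP 7.9.2 is triggered only if more than 5% withdraw consent.
- The under-reporting tipping point in SAP 7.10 uses scenarios 1, 2, 3 and 6. It omits scenario 9, and it adds missed events rather than lost survivor time.
- The other under-reporting analysis in SAP 7.10 moves CDM censoring back to the last health-system encounter and states no matching limit on deaths. This extends the asymmetry to participants who rely on CDM.

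So nothing in the plan removes it.

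**Size.** The plan gives no figure to reproduce, so this is an illustration.

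From the documents: 7,500 per arm, 38 months' enrollment and 50 months' maximum follow-up. With uniform accrual, follow-up C runs from 50 − 38 = 12 to 50 months, mean 31 months. Protocol Table 6 has an overall rate of 4.2% per year with relative risk 0.85, so the higher-risk arm has 4.2 × 2 / 1.85 = 4.54% per year.

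Assumed: 55% of that hazard is death, so λ = 0.55 × 4.54 ≈ 2.5% per year; 1% to 10% of participants are affected; their other sources end at 5% to 50% of follow-up (mean 27.5%), independently of outcome.

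*Affected group, all-cause death, per participant:*
- Probability of death: E[1 − exp(−λC)] = 0.0623.
- Full person-years: 0.0623 / 0.025 = 2.49.
- Person-years under the rule: 0.089 from those who die (full time) plus 0.275 × E[C·exp(−λC)] = 0.661 from survivors, total 0.750.
- Apparent rate: 0.0623 / 0.750 = 8.3% per year, against a true 2.5%.

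*Whole trial.* Share of person-time lost in the group: k = 1 − 0.750/2.49 = 0.70. With share q affected, the death rate is multiplied by 1/(1 − 0.70q):

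| q | Inflation of death rate |
|---|---|
| 1% | 0.7% |
| 3% | 2.1% |
| 5% | 3.6% |
| 10% | 7.5% |

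*Composite.* A Cox simulation (300 replicates per setting, sources ending in the first half of follow-up) moved the rate from 4.54 to 4.56, 4.63 and 4.74 per 100 person-years at 1%, 5% and 10% affected: increases of 0.4%, 2.0% and 4.4%.

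*Hazard ratio, same simulation:*

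| Affected share by arm | True HR | Composite HR | Death HR |
|---|---|---|---|
| equal (1%, 5% or 10%) | 1.00 | 1.00 | 1.00 |
| equal (1%, 5% or 10%) | 0.85 | 0.85 | 0.85 |
| 3% vs 5% | 1.00 | 1.01 | 1.02 |
| 5% vs 10% | 1.00 | 1.02 | 1.04 |
| 5% vs 10% | 0.85 | 0.87 | 0.89 |

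Stopping deaths and survivors at the same date returned the composite rate and hazard ratio to the truth, because that date was generated independently of outcome.

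*Short gap.* If sources end only 6 months before study end (assumed), about 6/31 = 19% of the group's time is lost. At q = 5% the inflation is about 1/(1 − 0.05 × 0.19) − 1 ≈ 1%.

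**The case against.** The strongest reply is about reach. SAP 7.5 takes the maximum across sources. The CDM date is set per site rather than at the last encounter, so a silent participant still runs to the site's date. Protocol III.A recruits through health systems, and III.C.5 plans CDM data for all participants. The scenario table lists potential combinations, classified by what was available for more than half of follow-up; it does not show that row 9 has anyone in it. This all stands, and it is why the point is minor. It does not remove the gap: the SAP states an expectation that study end will bind, and defines the other dates for when it does not.

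A reader might infer that everyone without CDM or claims, meaning rows 1 and 2 as well, is affected. The documents do not support that. Those participants self-report by definition. Participants without internet are followed by Call Center telephone and 7.5 lists no separate call date, so the portal's last point of contact plausibly covers direct calls. Someone found and spoken to then has a new contact date. What remains is survivors confirmed only through an alternative contact, a site or a locator service.

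A reader might also infer that the treatment comparison is biased. With equal shares and timing by arm the hazard ratio does not move. Open-label treatment makes a difference between arms possible, but nothing in the documents indicates one. SAP 7.9 plans to describe clinical events by availability of follow-up data and treatment group, which would help to expose it.

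Finally, leaving the vital-status date out is defensible for nonfatal endpoints. A report that someone is alive does not show freedom from hospitalization for MI, stroke or bleeding.

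**Conclusion.** The point holds in limited form. For participants whose late status is known only through a third party, and whose CDM, claims and portal dates stop before study end, SAP 7.5 makes follow-up depend on whether they died. Absolute death and composite rates and the cumulative incidence curves are inflated. Across the assumed shares the range is about 0.4% (composite, 1% affected) to 7.5% (death, 10% affected), resting on long gaps in follow-up, a 2.5% yearly death rate and source dates unrelated to outcome. A gap of about six months cuts the effect to roughly a quarter. Bias in the hazard ratio requires a difference between arms in share or timing; even 5% vs 10% moves the composite from 1.00 only to 1.02. The documents do not give the number affected. Severity: minor.

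**What to change.** 1. **All-cause death only.** Add the date last known alive from the vital-status check to the sources in SAP 7.5, and censor at the latest available date, capped at study end. The rules for consent withdrawal and limited participation stay as they are.
2. **Composite.** Keep the existing source dates, and do not treat an alive report as evidence of freedom from nonfatal events. Add one sensitivity run that counts deaths only up to each participant's last other source date, so that deaths and survivors share a cutoff. Apply the same cutoff to deaths in the last-encounter CDM analysis of SAP 7.10.
3. **Bleeding, MI and stroke.** Leave the censoring dates unchanged. Report the number of vital-status-only participants by arm.

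The cost is a sentence in 7.5, one date from the vital-status search, one extra run and a count. The downside is that the sensitivity run leaves out late deaths. Where the last source date is the participant's own last contact or encounter, death necessarily follows it, so the run should be read as a lower bracket beside the primary result, not as a replacement.

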7.6 Power

Calculations were performed using PASS software. For the primary effectiveness endpoint, power calculations were based on an estimated primary event rate of 5.5% per year (in the higher risk arm), annualized rate of loss to follow-up of 5%, two-sided significance level α of 0.05, 7,500 patients in each treatment arm, enrollment of 38 months and a maximum follow-up period of 44 months. The power of the chosen testing strategy to detect a statistically significant

difference under these assumptions is 85% if the relative risk reduction is 15%, corresponding to a total of 1246 primary effectiveness events.

In November 2019, the DSMB approved extended follow-up in response to updated power calculations based on observed primary event rates. Assuming 7,500 patients in each treatment arm, annualized rate of loss to follow-up of 5%, two-sided significance level α of 0.05, enrollment of 38 months and maximum follow-up period extended to 50 months, the power to detect a relative risk reduction of 15% is 88% when the overall primary event rate is 4.5% in the higher risk arm, corresponding to a total of 1322 primary effectiveness events.

For the primary safety endpoint, power calculations were based on an estimated primary event rate of 2.5% per year (in the higher risk arm), annualized rate of loss to follow-up of 5%, two-sided significance level α of 0.05, 7,500 patients in each treatment arm, enrollment of 38 months and a maximum follow-up period of 44 months. The power of the chosen testing strategy to detect a statistically significant difference under these assumptions is 81% if the relative risk reduction is 20%, corresponding to a total of 642 primary safety events.

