Assuming an annualized event rate of 4.6% in the higher risk arm and a 15% RR reduction (annualized event rate 3.8% in the lower risk arm) leads to 88% power and requires 1322 primary outcome events.

For the primary safety endpoint of hospitalization for major bleeding, power calculations were based on

Table 6					
Overall annualized event rate (%)	Relative Risk	Annualized event rate in low risk group (%)	Annualized event rate in high risk group (%)	Number of Events	Power
4.2	0.800	3.7	4.7	1321	0.99
4.2	0.825	3.8	4.6	1320	0.96
4.2	0.850	3.9	4.5	1322	0.88
4.4	0.800	3.9	4.9	1381	0.99
4.4	0.825	4.0	4.8	1381	0.97
4.4	0.850	4.1	4.8	1383	0.89
4.6	0.800	4.1	5.1	1441	0.99
4.6	0.825	4.2	5.0	1442	0.97
4.6	0.850	4.2	5.0	1439	0.90
4.8	0.800	4.3	5.3	1501	1.00
4.8	0.825	4.3	5.3	1502	0.98
4.8	0.850	4.4	5.2	1503	0.92

estimated primary event rates of 2%, 2.5%, and 3% per year (in the higher dose arm); annualized rate of loss to follow-up of 5%; 2-sided significance level alpha of 0.05; 7,500 participants in each treatment arm; total enrollment of 38 months; and a maximum follow-up period of 50 months. The power of the chosen testing strategy to detect a statistically significant difference in hospitalization for bleeding under these assumptions is shown in **Table 7**. Under all event rate scenarios, there will be power greater than 85% to detect an RR reduction of 25%, and for event rates of 2.5% or greater, power will be close to 80% to detect an RR reduction of 20%.

III.F.6. Secondary Endpoints

Secondary endpoints include the components of the primary endpoint, coronary revascularization procedures, quality of life, and functional status (Section III.A.5.a). Time-to-event outcomes will be analyzed using the same approach as the one used for the primary endpoint. Variables collected on numerical scales will be analyzed as continuous variables. Linear repeated measures mixed model will be employed to compare the 2 treatments on the changes from baseline.

Table 7			
Annualized event rate in higher-dose arm	Relative risk reduction	No. of events	Power
2%	25%	436	86%
	20%	449	66%
	15%	461	42%
2.5%	25%	544	92%
	20%	559	76%
	15%	575	50%
3%	25%	651	96%
	20%	669	83%
	15%	688	58%

III.F.7. Prior Treatment Effect

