Although the importance of understanding the effects of aspirin in these subgroups is critical, we recognize that despite enrolling 15,000 participants, our power to detect statistically significant and clinically meaningful interactions will be limited. However, this effort represents the largest such undertaking and is of vital importance. Heterogeneity of treatment effect will be established

Table 8		
Subgroup size as % of total	Relative risk reduction	Power
10%	25%	37%
	20%	25%
	15%	16%
30%	25%	81%
	20%	60%
	15%	38%
50%	25%	95%
	20%	82%
	15%	57%
70%	25%	99%
	20%	93%
	15%	71%
90%	25%	99%
	20%	97%
	15%	81%

based on the interaction test specified above. Testing for differences between treatment arms within subgroups will be considered exploratory, and no claims of heterogeneity will be made based on tests

within subgroups. By their nature, these tests have low power unless the effect sizes are large, as illustrated in **Table 8**.

Participants without internet access will not be analyzed as a pre-specified sub-group, but sensitivity analyses for the main trial endpoints will be incorporated into the SAP to analyze the populations with vs without internet access to assess the consistency of the treatment results and potential treatment interactions, given expected demographic and socioeconomic differences between the groups.

III.F.10. Interim Blinded Trial Monitoring

During the conduct of the trial, state of the art statistical monitoring techniques will be employed. These will be conducted in a blinded fashion. Study discontinuation patterns will be observed, as well as reasons for the missing data. The event rate will be monitored as it accumulates, and event rate projections will be developed to help us determine if and when we are likely to achieve sufficient power. Baseline characteristics of enrolled participants will also be reviewed to ensure that the population defined in the protocol is enrolled. The primary safety events will be monitored as they accumulate.

III.G. Study Coordination and Monitoring

III. G.1. Site Management and Quality Assurance

This trial will be monitored using quality-by-design principles and will not require on-site monitoring.

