The DSMB may recommend stopping the trial for any safety-related concern at any time. Particular attention will be paid to all-cause mortality. For effectiveness, the trial will compare doses of aspirin that have been proven effective in previous trials, and thus it is unlikely that any dramatic differences will appear early. However, the DSMB will monitor these differences about every 6 months over the 3.5 years of the trial. Thus, we anticipate 6 interim analyses and 1 final analysis. Because there are multiple tests, each test must be made at an adjusted alpha level using group sequential-testing methods. To minimize the chance of stopping early due to a spurious result, the endpoints will be tested at the planned analyses using a specific method known as the Haybittle-Peto rule. 101 This rule tests the

endpoints at the 0.001 level (z = 3.29, two-sided) at each interim review and then makes the final test at the 0.0499 level (z = 1.9605). Thus, there is only minimal penalty for interim analyses.

The decision-making structure and process for the DSMB will be described in a separate DSMB charter.

III.G.6. Data Auditing Conventions

Data will be collected via the study patient portal (Sections III.A.3.c and III.A.3.h).

IV. Human Subjects

IV.A. Protection of Human Subjects

IV.A.1. Sources of Data

Data obtained from the study participant web portal, from the CDM, from Centers for Medicare Services, and from HealthCore/Anthem Research Network, an HPRN, will be transferred to the DCRI along with unique participant identifiers. Details for the process and authorization for Medicare and health plan data linkages are contained in a separate Linkage Plan document. Data contained within the CDM will be obtained from each of the recruiting sites and the HPRN and will be transferred to the DCRI. The control of access to databases at DCRI will be managed centrally by the DCRI through user passwords linked to appropriate access privileges. This protects data from unauthorized view and modifications as well as inadvertent loss or damage. Within the secondary SAS databases, UNIX group access control will be used for maintaining similar security. The Sun workstation login will be secured by extensive user password facilities under UNIX.

IV.A.2. Potential Risks

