CDM data was extracted through queries issued by the DCRI data coordinating center for a prespecified number of times throughout and at the end of the trial. Claims data were collected periodically at a few specified time intervals.

4 Randomization and Drug Allocation

Patients were randomized via a patient portal in a 1:1 ratio to receive 81 mg vs. 325 mg of aspirin in an open-label fashion. Patients were asked to obtain their randomized aspirin dose at their local pharmacies. The randomization scheme was established before the inception of enrollment. Randomized treatment assignment has been obtained from the patient portal data. Compliance with the randomized aspirin dose assignment has been obtained from patient reported data.

Additionally, patients have been randomly assigned to follow-up intervals of every 3 vs 6 months. By embedding a secondary randomization for follow-up time intervals, the best methods for optimizing participant adherence, compliance, and retention in this pragmatic trial will be investigated.

5 Study Endpoints

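### The primary-endpoint power figures run 3 to 4 points above what the planned Cox/log-rank test gives at a hazard ratio of 0.85, the effect measure is not defined, and the worked example contradicts Table 6

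*SAP*

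**What the plan says.** SAP 7.6 gives two power statements for the primary endpoint, both calculated in PASS.

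- **44-month plan.** The inputs are 5.5% per year in the higher-risk arm, 5% annual loss, and "two-sided significance level α of 0.05, 7,500 patients in each treatment arm, enrollment of 38 months and a maximum follow-up period of 44 months". On these inputs, the SAP says, power "is 85% if the relative risk reduction is 15%, corresponding to a total of 1246 primary effectiveness events".
- **50-month plan.** With follow-up extended, "the power to detect a relative risk reduction of 15% is 88" per cent "when the overall primary event rate is 4.5% in the higher risk arm, corresponding to a total of 1322 primary effectiveness events".

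Protocol III.F.5 describes the second scenario with 4.6% per year in the higher-risk arm and says that "a 15% RR reduction (annualized event rate 3.8% in the lower risk arm) leads to 88% power and requires 1322 primary outcome events". Table 6 has a row with the same power and event count: overall rate 4.2%, relative risk 0.850, arm rates 3.9% and 4.5%.

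The power sections call the effect a relative risk or a relative risk reduction, never a hazard ratio, and do not name the PASS procedure. The primary test is a Cox model, described as equivalent to the log-rank test (protocol III.F.3, SAP 7.3).

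**The concern.** The power of a log-rank test depends essentially on the number of events and the hazard ratio. The unpublished accrual pattern therefore does not prevent a check, because the event counts are given. At a hazard ratio of 0.85 the stated counts do not yield the stated power.

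The 50-month scenario is also described in three ways: 4.6% against 3.8% (protocol text), 4.5% against 3.9% (Table 6), and an overall rate of 4.5% in the higher-risk arm (SAP). Table 6 separates the overall rate from the higher-arm rate.

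The trial will report a hazard ratio. A reader who sets it beside 88% power for a 15% reduction would put the chance of missing a true hazard ratio of 0.85 at 12%. With 1322 events it is about 16%.

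**Working it through.** **Inputs.** Two-sided alpha 0.05 and 7,500 per arm (SAP 7.6); 1:1 allocation (SAP 4); effect 0.85; event counts 1246 and 1322 (SAP 7.6) and those in Table 6.

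**Step 1. Reading that reproduces the stated figures.** Treat 0.85 as the ratio of cumulative event proportions. With d events in total, p1 = d / (7500 × 1.85), p2 = 0.85 × p1, and the implied hazard ratio is ln(1 − p2) / ln(1 − p1).

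- d = 1322: p1 = 0.0953, p2 = 0.0810, HR = 0.8435. Power is 87.2% (87.0% by a two-proportion test); stated 88%.
- d = 1246: p1 = 0.0898, p2 = 0.0763, HR = 0.8439. Power is 85.0% (84.8% by a two-proportion test); stated 85%.

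All 12 rows of Table 6 come out within about 1 point on this reading.

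**Step 2. Reading that matches the planned test.** Take 0.85 as the hazard ratio and use Schoenfeld's formula: power = Φ(½ √d × |ln HR| − 1.96), with |ln 0.85| = 0.1625.

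- d = 1322: ½ × 36.36 × 0.1625 − 1.96 = 0.995, so power is 84.0%.
- d = 1246: ½ × 35.30 × 0.1625 − 1.96 = 0.908, so power is 81.8%.

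| Source | Events | Stated | HR 0.85 | Cumulative ratio 0.85 |
|---|---|---|---|---|
| SAP, 44 months | 1246 | 85% | 81.8% | 85.0% |
| Table 6, overall 4.2% | 1322 | 88% | 84.0% | 87.2% |
| Table 6, overall 4.4% | 1383 | 89% | 85.6% | 88.7% |
| Table 6, overall 4.6% | 1439 | 90% | 86.9% | 90.0% |
| Table 6, overall 4.8% | 1503 | 92% | 88.3% | 91.3% |

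**Step 3. Other conventions** (1322 and 1246 events respectively).

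- Freedman's formula: 83.8% and 81.6%.
- Final-look alpha 0.0499 (protocol III.G.5): 84.0% and 81.8%.
- Simulated log-rank test, 4,000 runs: 83.7% and 81.9%.
- One-sided 0.05: 90.5% and 88.9%, which overshoots.
- Annual rates read as annual probabilities (HR about 0.847): 85.5% and 83.8%, still 2.5 and 1.2 points short.

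At HR 0.85, 85% power needs about 1360 events and 88% about 1489.

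**Step 4. The worked example.** 3.8 / 4.6 = 0.826, a 17.4% reduction. Rounding does not rescue it: the largest ratio that rounds to these rates is below 3.85 / 4.55 = 0.846. A 15% reduction from 4.6% is 4.6 × 0.85 = 3.91%. In Table 6 the pair 4.6% and 3.8% is the 0.825 row at overall rate 4.2%, with 1320 events and 96% power. The 0.850 row at that overall rate shows 4.5% and 3.9%. The example therefore attaches one row's power and event count to another row's rates.

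**The case against.** The strongest reply is that the documents say relative risk, not hazard ratio. Read as a ratio of cumulative proportions, the figures are coherent: both SAP pairs and the whole of Table 6 reproduce. This stands, and it rules out saying that the stated power simply cannot come from the stated counts. It does not remove the problem, because neither document states that reading. Table 6 sets the relative risk beside annualized rates with about that ratio, the planned model estimates a hazard ratio, and the Bayesian thresholds in SAP 7.10 are hazard ratios. The safety figure in SAP 7.6 (642 events, 20% reduction, 81%) gives 80.7% as a hazard ratio and 82.1 to 82.4% as a cumulative ratio, so it does not favour the cumulative reading, though the difference is too small to decide.

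A second reply is that the event counts, not the power, may be wrong. This also stands. Assuming uniform accrual, the stated rates and 5% loss give about 1407 to 1440 events at 44 months (86 to 89% power) and 1417 to 1443 at 50 months (86 to 88%). Protocol III.F.5 says the updated calculation used actual accrual, but does not give the pattern.

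Two stronger readings are tempting and not supported.

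- **That Tables 6 and 8 contradict each other.** Table 8's 90% subgroup shows 81% for a 15% reduction, close to the 80.0% from 0.9 × 1322 events at HR 0.85. But Table 8 states no event count, and 0.9 × 1246 events under the cumulative reading gives 81.1%.
- **That the choice of 15,000 patients and 50 months rests on the 88%.** Protocol III.F.5 cites enrollment feasibility, expected event rate and meaningful risk reduction. SAP 7.6 says updated power calculations prompted the extension, but neither document sets 88% as a threshold.

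**Conclusion.** The concern holds in two parts.

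First, the effect measure behind the power figures is undefined. Taken as HR 0.85 for the planned test, the power is 84.0% instead of 88% for 1322 events and 81.8% instead of 85% for 1246, and the 0.85 rows of Table 6 are high by about 3 to 4 points. Taken as stated, the powers belong to a hazard ratio of about 0.843. This rests on proportional hazards, 1:1 allocation and the stated event counts. Which of power, event count or effect measure is off cannot be settled from the documents.

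Second, the protocol's 4.6% and 3.8% example is wrong against the protocol's own table under any reading, and the SAP merges the overall rate with the higher-arm rate.

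This is a reporting error of modest size, not a design failure. Power exceeds 80% on every two-sided reading examined of a 15% reduction, and no analysis or stopping rule changes.

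**What to change.** In SAP 7.6, protocol III.F.5 and Table 6:

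1. State the effect measure and the PASS procedure used.
2. Then either restate power at HR 0.85 as about 84% (1322 events) and 82% (1246 events) and recompute the other rows from their counts, or keep the given powers and say that they apply to a hazard ratio of about 0.843 where the relative risk is listed as 0.85.
3. Correct the protocol's worked example to 4.5% against 3.9%.
4. Reword the SAP rate as 4.5% in the higher-risk arm, with an overall rate of 4.2%.

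The cost is a text and table correction. No patients or follow-up are added. If power is restated at HR 0.85 it looks slightly less favourable but remains above 80%.
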